#### Cardiac MRI:

Cardiac MRI will be performed with a 1.5- or 3.0-Tesla MRI scanner (Siemens Medical Solutions, Forchheim, Germany). Imaging is performed during breath-hold at end-expiration. During the procedure, ECG is continuously monitored. After acquisition of scout views for the determination of the standard orientations of the heart, cine images will be acquired for functional evaluation and measurements (4 chamber, 2 chamber, short axis). T1 acquisitions are performed before and after injection of 0.2 mmol/kg gadoterate meglumine (Dotarem, Guerbet, Villepinte, France). T1 mapping is a parametric quantitative sequence, which provides tissue-specific T1 values. For T1 mapping, a 5(3)3 sampling scheme of the heart is performed,

using a modified Look Locker sequence. Pixel-wise T1 maps of the myocardium are acquired in 3 short-axis views with inline motion correction. The major advantage of T1 mapping sequences is their potential for quantitative objective assessment of myocardial abnormalities. Myocardial pathologies leading to T1 changes include diffuse myocardial fibrosis, edema, inflammation, and infiltrative diseases such as amyloidosis, Fabry disease, and hemosiderosis. The comparison of T1 values before and after Gadolinium enable the quantitative estimation of myocardial interstitial remodeling and extracellular space expansion, to evaluate myocardial extracellular volume. Ten minutes after the Gadolinium injection, a late Gadolinium enhancement (LGE) series is performed to assess possible myocardial infarction and gross fibrosis. Image post-processing includes the measuring of cardiac dimensions, ventricular volumes, LV and RV function, LV mass, and T1 tissue values.

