## **2. OBJECTIVES**

Primary Objectives:

The main objective of this study is to determine the most suitable diagnostic test to identify cardiopulmonary (dys)function in EC survivors treated with neo-CRT followed by surgical resection. Furthermore, we want to estimate the difference in cardiopulmonary (dys)function in EC survivors treated with neo-CRT followed by surgical resection compared to EC survivors who were treated with surgical resection alone.

1. To determine the differences in clinical cardiac and pulmonary events, (cardiac ischaemia, heart failure, arrhythmia, valve disorders, pulmonary hypertension, COPD) as clinically diagnosed since treatment between patients treated with neo-CRT and surgery alone.
2. To determine the difference in other (subclinical) parameters as tested by echo cardiogram, 6 minute walking test, CT scan, MRI scan and biomarkers.
3. To analyse the current CAC scores in both patient groups.
4. To determine the difference between the baseline and current CAC scores.

5. To determine the difference between ECG findings currently and on baseline.
6. To correlate the different subclinical imaging parameters to the radiation dose given to the heart and lungs
7. To correlate CAC scores with the given dose distribution on plannings CT scan

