## 7. SAMPLE SIZE CALCULATION

As this is a pilot study to determine (sub-clinical) cardiopulmonary toxicity, a total of 40 patients, 20 in each group, will be included in this study.

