## **10. STATISTICAL ANALYSIS**

### **10.1. Primary study parameter(s)**

Different cardiopulmonary parameters will be presented by means and standard deviations and will be compared between the groups using an independent t-test, with Bonferroni correction if applicable.

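### Cardiac MRI may be done at 1.5 or 3.0 Tesla while T1 is compared by an unadjusted t-test; if both scanners are used, the T1 comparison loses precision

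*Protocol*

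**What the plan says.** Under the Cardiac MRI heading in section 8.2 the protocol states: "Cardiac MRI will be performed with a 1.5- or 3.0-Tesla MRI scanner". It does not say which patients go to which scanner, or that one scanner serves all of them. The same paragraph presents T1 as an absolute quantity: "T1 mapping is a parametric quantitative sequence, which provides tissue-specific T1 values", and "The major advantage of T1 mapping sequences is their potential for quantitative objective assessment of myocardial abnormalities". T1 is among the measured outputs: "Image post-processing includes the measuring of cardiac dimensions, ventricular volumes, LV and RV function, LV mass, and T1 tissue values". Pre- and post-contrast T1 also feed the extracellular volume (ECV): "The comparison of T1 values before and after Gadolinium enable the quantitative estimation of myocardial interstitial remodeling and extracellular space expansion".

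Section 2 places the group comparison of MRI parameters under the primary objectives (item 2): "To determine the difference in other (subclinical) parameters as tested by echo cardiogram, 6 minute walking test, CT scan, MRI scan and biomarkers". Section 10.1 gives the method: "Different cardiopulmonary parameters will be presented by means and standard deviations and will be compared between the groups using an independent t-test", with a Bonferroni correction where it applies. Section 7 fixes the size: "a total of 40 patients, 20 in each group, will be included in this study". Appointments are made patient by patient after consent (section 8.2). Nothing in the protocol balances scanner use between the groups or brings field strength into the analysis.

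**The concern.** That T1 relaxation time changes with magnetic field strength is general MR physics. The protocol does not say so, but the point needs no outside study result. Values acquired at 1.5 T and 3.0 T are therefore not on one scale. A two-sample t-test on pooled values treats the offset between scanners as if it were variation between patients.

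The pilot is meant to identify the most suitable test for a later cohort study. If the scanners are mixed, T1 mapping could look less discriminating than it is, for a reason that has nothing to do with the patients. If scanner use also differed between the treatment groups, part of the observed T1 difference would come from the scanner.

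**Working it through.** **Inputs from the protocol.** Two field strengths are permitted (8.2), there are 20 patients per group (7), and the test is an independent t-test on means (10.1). The protocol states no alpha, power, SD or effect size for its sample size, so it has no figure of its own to reproduce.

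**Assumed inputs.** Two-sided 5%; a true group difference of 0.8 within-field SD; a field offset k of 1, 2 or 4 within-field SDs; a share p of patients at 3.0 T.

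**1. Precision with scanners used at random, p = 0.5.**
- Pooled SD in within-field units = √(1 + k²·p·(1−p)) = √(1 + k²/4).
- Effective n per group = 20 / (1 + k²/4).
- Standardised difference = 0.8 / pooled SD.
- Power comes from the noncentral t with 38 degrees of freedom and noncentrality (standardised difference)·√(20/2).

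| Offset k | Pooled SD | Effective n per group | Standardised difference | Power |
|---|---|---|---|---|
| 0 (one field strength) | 1.00 | 20 | 0.80 | 69% |
| 1 | 1.12 | 16 | 0.72 | 60% |
| 2 | 1.41 | 10 | 0.57 | 41% |
| 4 | 2.24 | 4 | 0.36 | 20% |

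**2. Precision with an exact 10:10 split in both groups.** The offset then cancels from the mean difference but still inflates the SD that the test uses, so the test becomes conservative. Simulated power is about 60%, 36% and 2% for k = 1, 2 and 4.

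**3. A less even mix.** With p = 0.1 the pooled SD is √(1 + 0.09·k²) = 1.04, 1.17 and 1.56, and power is 66%, 56% and 35%. With p = 0 or 1 nothing is lost.

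**4. Type I error when scanner use is unrelated to group.** With 20 of the 40 patients at 3.0 T, allocated at random, the simulated rejection rate under no true difference is about 5% for all three offsets. The plain t-test keeps its level.

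**5. Bias when scanner use differs between groups.**
- Shift in the mean difference = k × (share at 3.0 T in one group − share in the other).
- For 12 v 8: k × (12/20 − 8/20) = 0.2k, that is 0.2, 0.4 or 0.8 SD. A split at least this uneven has a 34% chance under random use (hypergeometric, 20 of 40 at 3.0 T). Type I error at this split is only about 6%, 6% and 3%, because the inflated SD offsets the shift.
- For 14 v 6: type I error is about 18%, 41% and 76%, but a split this uneven or worse has only a 2.6% chance under random use.

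**6. Does adjustment recover the loss?** With field strength as a covariate, power for 0.8 SD is 69% at 10 v 10, 68% at 12 v 8 and 62% at 14 v 6, whatever the offset. Adjustment recovers nearly everything unless scanner use is strongly tied to group.

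**The case against.** - **The wording may mean one scanner for everyone.** That reading is possible, and the problem would then disappear. The text does not settle it, and one sentence would.
- **The offset, the mix and the power benchmark are all assumed.** This stands. The size can be given only as a range, an even mix is the costliest for variance, and the protocol sets no power target for T1.
- **A statistical analysis plan could add a scanner term.** This stands in part. Such a plan may exist and is not shown. The choice of scanner, however, belongs to the protocol, and section 10.1 already names an unadjusted test.
- **The scope is narrow.** This stands. The concern applies to native and post-contrast T1. It is weaker for ECV, which is built from T1 changes and hematocrit, and it does not extend to ventricular volumes, function or mass. T1 is one family of parameters among many in an exploratory pilot.

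A reader might go further and infer that the plan produces false-positive T1 differences. The documents do not support that. Patients of both groups come from one centre and are booked individually, and nothing ties scanner choice to treatment group. Under random use the overall type I error stays near 5%. The 34% chance belongs to a 12 v 8 split and must not be paired with the high error rates, which belong to a 14 v 6 split.

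**Conclusion.** The point holds as a matter of precision, and only if both field strengths are actually used. The protocol then pools T1 values from two scales and tests them without adjustment. With a random even mix and an offset of 1 to 4 within-field SDs, power for a 0.8 SD difference falls from 69% to between about 60% and 20%. An exact 10:10 split at the largest offset would bring it to about 2%.

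Bias is a conditional risk: it needs scanner use to differ between groups, and large false-positive rates need a strong imbalance that chance alone rarely produces. What is affected is the raw T1 comparison and the standing of T1 mapping among the candidate tests, not the study as a whole. The change is cheap and should be made before scanning, because later adjustment recovers less if scanner use turns out to be tied to group.

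**What to change.** In the Cardiac MRI paragraph of section 8.2, state that all patients have T1 mapping at one field strength. If that is not possible for a patient, record the field strength. In section 10.1, for the T1 comparisons only, replace the plain t-test by a comparison with field strength as a covariate, or standardise T1 within field strength first.

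The cost is one or two sentences, plus slightly less flexibility in booking scanner slots or, where adjustment is used, one degree of freedom. No extra scan is needed.

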#### *Anamnesis and physical examination:*

The patients will be interviewed on matters concerning their medical history, cardiopulmonary complaints and patients will be asked to fill in the following questionnaires: EORTC ACE27, EORTC LC13, EuroQOL 5D and the EORTC C30. A general physical examination will be performed, including length and weight.

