#### *6 minute walking test:*

Gives an estimate of the general functioning status of the patients during follow up. It is known to correlate with maximum oxygen uptake and physical fitness without laboratory test [24].

*Laboratory tests:*

NT pro BNP and hs TNT are known markers in cardiology for myocardial damage and “volume overload” like in diastolic dysfunction. Blood markers like cholesterol, CRP, HbA1 will help determining the baseline risk on cardiac events. eGFR will be checked before gadolinium is infused in order to minimize risks on its possible side effects. It is necessary to determine hematocrit for calculation of the extracellular volume (ECV).

*ECG*

Simple screening instrument to indicate hypoxia, pericarditis, past infarctions, bundle branch blocks and rhythm disorders

*Echocardiogram:*

An echocardiogram is performed as a safe non-invasive screening technique, which is able to measure hypertrophy of the myocardium, pericarditis, wall motion disorders, blood flows and pressures, which are functional parameters who could indicate pulmonary hypertension and diastolic- or systolic dysfunction and valve disorders[25].

The echocardiographic assessment will be performed by the Echocardiography Core lab ([www.G-ICL.com](http://www.G-ICL.com)) facility, of the UMCG. The echocardiographic protocol includes assessments of systolic and diastolic function of both ventricles according to the guidelines of the European Association of Cardiovascular Imaging (EACVI). Specifically we will assess:

1. Tricuspid annular plane systolic excursion (Tapse)
2. Velocity of the tricuspid annular systolic motion (RV s')
3. Right ventricle fractional area change
4. Doppler notching of right ventricular outflow tract signal
5. Tricuspid valve Doppler velocity
6. Pulmonary valve Doppler velocity
7. Myocardial performance index (Tei index)
8. Pulmonary artery acceleration time
9. Pulmonary valve end diastolic velocity
10. Cardiac Output
11. Left ventricle systolic function

- 12.Left ventricle diastolic dysfunction
- 13.Valvar abnormalities
- 14.Left ventricle eccentricity index
- 15.Right ventricle strain
- 16.Right atrium volume
- 17.Inferior Caval Vein collapsibility

Also 2D strain echocardiography will be performed to establish subtle changes in myocardial function.

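### Section 10.1 fixes an unadjusted t-test for size-dependent cardiac measures and for NT-proBNP and hs-TNT, although age, sex, length, weight and eGFR are all recorded

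*Protocol*

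**What the plan says.** Section 10.1 sets one method for the primary parameters: "Different cardiopulmonary parameters will be presented by means and standard deviations and will be compared between the groups using an independent t-test". The only qualification is a clause on multiplicity, "with Bonferroni correction if applicable". It names no covariate and no scaling.

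The parameters include several that plausibly depend on body size. The Cardiac MRI part of section 8.2 states: "Image post-processing includes the measuring of cardiac dimensions, ventricular volumes, LV and RV function, LV mass, and T1 tissue values". The echocardiogram list in the same section adds right atrium volume and cardiac output. The blood tests add two cardiac markers: "NT pro BNP and hs TNT are known markers in cardiology for myocardial damage". Objective 2 in section 2 makes these group comparisons an aim: "To determine the difference in other (subclinical) parameters as tested by echo cardiogram, 6 minute walking test, CT scan, MRI scan and biomarkers".

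The variables needed for a better comparison are already collected:

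- **Age and sex** are listed in section 4.
- **Body size** is recorded at the visit: "A general physical examination will be performed, including length and weight".
- **Kidney function** is measured for contrast safety: "eGFR will be checked before gadolinium is infused in order to minimize risks on its possible side effects".

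Section 10.2 only tabulates risk factors and tests them between groups; it does not carry them into the outcome comparison. Section 1 (Patient population) expects the groups to be comparable because patients were not selected on co-morbidity or age. Sections 6.1 and 7 set 20 patients per group without matching.

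**The concern.** An unadjusted t-test puts all variation from body size, sex and age into the error term. For LV mass or a ventricular volume that share may be large, and with 20 per group there is little precision to spare.

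The groups were not randomised. The reason given for expecting balance does not mention sex, body size or kidney function. Section 1 says neo-CRT became standard in 2012, so the surgery-alone patients may on average have been treated earlier, with consequences for current age. Section 6.1 dismisses length of follow-up because surgery is not regarded as a late-toxicity risk, which does not deal with ageing. Imbalance is therefore plausible, though not established, and it could push a difference in either direction.

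The pilot's purpose is to choose tests for a later cohort study. A size-dependent measure analysed this way carries noise that a tissue measure such as T1 does not carry to the same degree. The ranking of tests could partly reflect body size rather than diagnostic value.

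**Working it through.** The plan has no power calculation to reproduce: section 7 gives 40 patients with no alpha, effect size or SD. Two-sided alpha of 5% and 80% power are assumed below.

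**Precision without adjustment (n = 20 per group)**

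- Normal approximation: (1.96 + 0.84) × √(2/20) = 0.89 SD.
- Exact t (38 degrees of freedom): 0.91 SD.
- If the Bonferroni correction covered 10 to 30 tests (number assumed): 1.22 to 1.35 SD.

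**Precision with covariates explaining a share R² of the variance**

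The detectable difference is 0.909 × √(1 − R²), and the equivalent unadjusted group size is 20/(1 − R²). R² is assumed. Power is a normal approximation.

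| R² | Detectable difference (SD) | Equivalent n per group | Power for 0.8 SD |
|---|---|---|---|
| 0 | 0.91 | 20 | 72% |
| 0.2 | 0.81 | 25 | 81% |
| 0.4 | 0.70 | 33 | 90% |
| 0.5 | 0.64 | 40 | 95% |

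These figures ignore the one or two degrees of freedom spent and any correlation between covariate and group. Both make the real gain somewhat smaller. Indexing by a ratio also need not remove the whole R² that a regression would.

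**Spurious difference from sex mix, LV mass as the example**

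Assumed: men exceed women by 30-40 g, SD 25-30 g, and the groups are 90% and 70% men.

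- Shift in means: (0.90 − 0.70) × 30 = 6 g, to 0.20 × 40 = 8 g.
- In SD units over the full range of assumptions: 6/30 = 0.20, to 8/25 = 0.32.

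**How often that would mislead**

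In a simulation of 40,000 trials per setting with no true group effect and a sex effect of 1.0-1.5 within-sex SD:

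| Men in each group | Bias (SD) | Unadjusted t-test rejects | Model with sex rejects |
|---|---|---|---|
| 15 v 15 | 0 | 3.3% to 1.9% | about 5% |
| 17 v 13 | 0.20 to 0.30 | 6.8% to 8.1% | about 5% |
| 18 v 12 | 0.30 to 0.45 | 11.3% to 17.7% | about 5% |

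The first row shows the precision loss alone: with perfect balance the unadjusted test is conservative. The gap of four men in the second row is the same as 90% v 70% of 20 (18 v 14).

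For a continuous covariate with R² of 0.2-0.5, the bias is √R² × the group shift in covariate SDs. A shift of 0.5 SD gives a bias of 0.22-0.35 SD and 10-19% false positives; a shift of 0.3 SD gives 6-10%.

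If both groups are random draws from one population (75% men assumed), the unadjusted test rejects 5.0% overall, although a gap of four or more men arises in about 20% of such samples.

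**The case against.** Several counter-arguments have force.

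- **Raw values.** A reader might infer that the protocol commits to un-indexed MRI and echo values. It does not: it is silent. Indexing is a derivation detail that may sit in an analysis plan or imaging manual not at hand, and recording length and weight is compatible with it. What stands is the stated test in section 10.1, which is unadjusted.
- **Reach.** A reader might take the point to cover all candidate tests. The endpoints in section 3 do not name LV mass or chamber volumes, and many echo items are ratios, velocities, timings or strain. These, and T1, are not affected in the same way.
- **False positives.** A reader might conclude that the plan inflates the type I error. Chance imbalance alone leaves it at 5% on average. A false difference needs actual imbalance, and section 10.2 would show some of it, although showing it is not adjusting for it. The precision loss needs no imbalance.
- **Kidney function.** A reader might argue that chemotherapy lowered eGFR in the neo-CRT group, so that raised NT-proBNP there need not be cardiac. The protocol neither says so nor specifies the drugs this cohort received. If it were true, current eGFR would be a consequence of treatment, and adjusting for it could remove part of the effect sought. That argues against eGFR as a required covariate.
- **Sample size.** Forty patients in an exploratory pilot support only one or two covariates per model. This limits the fix but does not remove the case for it.

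**Conclusion.** The point holds as a modest, nearly free improvement to a stated method; it is not an internal contradiction. Section 10.1 prescribes an unadjusted comparison, in small non-randomised groups, of measures that plausibly depend on body size, sex, age or kidney function, while those variables are recorded and not used for the comparison.

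The likely gain is a detectable difference of about 0.81-0.64 SD instead of 0.91 SD, if covariates explain 20-50% of the variance. The possible bias is 0.20-0.32 SD for LV mass under the assumed sex difference, SD and sex mix. The protocol supplies none of these inputs, nor the dependence on size, sex, age and kidney function itself, so the figures indicate scale only. The finding is confined to ventricular volumes, LV mass, right atrium volume, cardiac output, NT-proBNP and hs-TNT.

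**What to change.** Add a few lines to section 10.1:

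1. Analyse ventricular volumes, LV mass, right atrium volume and cardiac output indexed to body surface area, in a linear model with group and sex. The sex term is needed because indexing alone is not shown to remove a sex difference. Repeat with height-indexed values as a check.
2. Analyse NT-proBNP and hs-TNT in a model with group and age. Show the eGFR-adjusted result beside it as a sensitivity analysis, because current eGFR is measured after treatment.
3. Leave T1, strain and ratio measures outside this change.

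No additional data are required. The cost is one or two degrees of freedom per model. Body-surface indexing is sensitive to weight loss, which is why the height-indexed check is included.

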#### ***Radiotherapy treatment plan***

The radiotherapy details, CT scan and delineated structures will be transferred to our current planning system in order to extract dose distributions and dose to the critical organs as, dose volume histograms will be exported. The cardiac CT scan will be co registered to our planning CT scan in order to correlate high dose regions to present coronary artery disease .

Participants will be in the hospital for 6-8 hours, including waiting time in between the tests.

In case, a clinically relevant, (subclinical) abnormality is diagnosed we will contact the patient and its general practitioner. The possible clinical consequences will be discussed with the cardiologist involved, and, if indicated, the patients will be referred to the cardiologist for further analyses or preventive measures.

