#### Cardiac CT imaging :

CT imaging will be performed on a latest generation dual-source CT scanner (Siemens Medical Solutions, Forchheim, Germany). A non-enhanced CT high pitch spiral acquisition in diastole with prospective electrocardiography (ECG) triggering will be performed with a standard protocol (120 kV tube potential; ref mAs 75) with an associated radiation dose of 0.6 mSv (less than a third of the annual background radiation dose). On the CT acquisition, the amount of coronary calcification will be calculated and expressed as a Coronary Artery Calcium (CAC) score based on the Agatston method.

The CAC score can be used to compare the current and baseline status (using the diagnostic CT scans performed before treatment) and is a reliable instrument for coronary disease [26]. Furthermore, dose distributions can be correlated with the coronary artery calcifications by fusing diagnostic CT scans with the planning CT scans in irradiated patients.

The CAC score at baseline will be used to estimate the baseline risk on cardiac events

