### **10.2. Other study parameters**

Risk factors for cardiac and pulmonary complaints will be presented in frequency tables and tested for statistical significant differences between both groups using an independent t-test

Location of focal wall abnormalities and arteriosclerosis and its relation to high dose regions will be presented in a table.

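### The dose analysis of coronary calcium does not account for calcium that predates radiotherapy, although a pre-treatment CAC score is already planned, and section 8.2 is unclear about which CT is registered to the planning CT

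*Protocol*

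**What the plan says.** Three places in the protocol link dose to coronary calcium.

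- Section 2, objective 7: "To correlate CAC scores with the given dose distribution on plannings CT scan". It does not say whether the score is the baseline one, the current one or the change.
- Section 8.2, Radiotherapy treatment plan: "The cardiac CT scan will be co registered to our planning CT scan", and the purpose is "in order to correlate high dose regions to present coronary artery disease". The outcome is disease as it stands at the study visit.
- Section 8.2, Cardiac CT imaging: dose can be related to calcification "by fusing diagnostic CT scans with the planning CT scans in irradiated patients".

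The protocol also plans a pre-treatment score. In the Cardiac CT imaging paragraph: "The CAC score can be used to compare the current and baseline status (using the diagnostic CT scans performed before treatment". The same paragraph uses the baseline score to estimate baseline cardiac risk, and objective 4 reads "To determine the difference between the baseline and current CAC scores". None of these stated uses is tied to dose.

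**The concern.** A coronary artery that was calcified before radiotherapy is normally still calcified years later. Its calcium enters the current score but cannot be an effect of the dose. A correlation of dose with current CAC therefore mixes what dose might have caused with what was there already.

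There are two consequences. If earlier calcium is unrelated to dose, it acts as noise and pulls the correlation toward zero. If it is related to dose, for whatever reason, it can produce a correlation when radiation has no effect.

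Pre-treatment calcium is plausible here: section 1 describes many of these patients as older, with cardiopulmonary problems from age, co-morbidity or lifestyle. Section 11.4 says that the most promising tests go forward into a cohort study of correlations with dose metrics. A diluted or spurious CAC signal could thus lead to CAC being dropped or promoted for the wrong reason.

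The registration step adds an uncertainty. The Cardiac CT imaging paragraph uses the term diagnostic CT for scans made before treatment, and in the next sentence fuses diagnostic CT scans with the planning CT. The Radiotherapy treatment plan paragraph registers the cardiac CT. A reader cannot tell whether one scan or both are placed on the dose grid.

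**Working it through.** **Inputs from the protocol.** 20 irradiated patients (section 7: 40 in total, 20 in each group). The protocol gives no baseline-current correlation, dose effect or significance level for this analysis, so there is no figure of its own to reproduce.

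**Assumptions.** Two-sided 5% test. CAC on a scale such as log(CAC+1), treated as normal with equal spread at both times. Baseline-current correlation r = 0.5, 0.7 or 0.8. Correlation of dose with new calcification 0.60 in case 1 and zero in case 2. Dose-baseline correlation q of zero in case 1 and 0.2 to 0.4 in case 2.

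**Model.** With B the standardised baseline score and E the new part, current C = r·B + √(1−r²)·E. The change is C − B, with variance 2(1−r).

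**Case 1: dose correlates 0.60 with E and is unrelated to B.**

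- Current CAC: 0.60·√(1−r²).
- Change: 0.60·√((1+r)/2).
- Current CAC adjusted for baseline: partial correlation 0.60.

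Power is by Fisher's z, with standard error 1/√17 for a simple correlation in 20 patients and 1/√16 for the partial correlation. Example at r = 0.7: atanh(0.428) = 0.458; 0.458 × √17 = 1.89; 1.89 − 1.96 = −0.07; power 47%. Adjusted: atanh(0.60) = 0.693; 0.693 × 4 = 2.77; 2.77 − 1.96 = 0.81; power 79%.

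| r | Current CAC | Change | Adjusted |
|---|---|---|---|
| 0.5 | 0.52 (66%) | 0.52 (66%) | 0.60 (79%) |
| 0.7 | 0.43 (47%) | 0.55 (73%) | 0.60 (79%) |
| 0.8 | 0.36 (34%) | 0.57 (76%) | 0.60 (79%) |

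**Case 2: dose has no effect but correlates q = 0.2 to 0.4 with B.**

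- Current CAC shows r·q. From 0.5 × 0.2 = 0.10 to 0.8 × 0.4 = 0.32, the test rejects in 7% to 28% of studies.
- Change shows −q·√((1−r)/2). It rejects in 6% to 13%. At r = 0.5 this is −0.5q, the same size as for current CAC, so both reject in 7% to 13%.
- Adjusted for baseline, the expected partial correlation is zero and the test keeps 5%.

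**Cost of missing scans (case 1).** With 16 of 20 scans scoreable, adjusted power uses √(16−4) = 3.46: 0.693 × 3.46 − 1.96 = 0.44, so 67%. With 12 of 20 it uses √8 = 2.83: 0.693 × 2.83 − 1.96 = 0.00, so 50%. The unadjusted figures in all 20 are 66%, 47% and 34% at the three values of r. At r = 0.5, losing four scans uses up the gain in power; at r = 0.7, losing eight nearly does. The protection against a spurious correlation remains.

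**The case against.** **The scans need not conflict.** If the pre-treatment CT and the current CT are both registered to the planning CT, the two paragraphs of section 8.2 complement each other and supply the images needed to tell old calcium from new. If diagnostic only means not the planning scan, they agree. This stands. A reader might infer that the protocol contradicts itself, or that it means to correlate dose with calcium that predates it. Neither paragraph excludes the other scan, so the text supports only a request to clarify.

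**Baseline CAC is not ignored.** This is correct. A reader might infer that the pre-treatment score goes unused, but it serves the baseline-to-current comparison and the estimate of baseline risk. The gap is confined to the dose analysis.

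**This is detail for a statistical analysis plan.** Partly so. However, the protocol itself fixes disease as it stands now as the outcome for the dose link, and it already plans the score that would correct this.

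**The group comparison has the same fault.** A reader might extend the point to the t-test in section 10.1. The documents do not carry that. The main objective says "we want to estimate the difference in cardiopulmonary (dys)function in EC survivors treated with neo-CRT followed by surgical resection" compared with surgery alone, objective 4 sits under it, and section 10.1 can already contrast the change. Section 1 expects comparable groups, in which case the t-test is valid. Which adjusted group model to use is debatable, and silence on it is not an error.

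**The location table.** Section 10.2 states "Location of focal wall abnormalities and arteriosclerosis and its relation to high dose regions will be presented in a table". The table is descriptive and claims no test. Marking earlier lesions in it, or tabulating segments in the surgery-alone group, would need reading beyond the planned score and is a matter of preference.

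**The figures are assumed and the study is exploratory.** Both are true. They limit the weight of the point; the direction of the effect does not depend on them.

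**Conclusion.** The concern holds for the dose-CAC correlation. As worded, it counts calcium that predates radiotherapy, while the score that would separate this calcium is already planned for other uses. Under the assumed correlations, a real association of 0.60 would appear as 0.52 to 0.36, with power of 66% to 34% against 79% adjusted. A null effect would be declared significant in 7% to 28% of studies if dose is related to baseline calcium at 0.2 to 0.4. These sizes rest entirely on assumed values and on a normal model for a score that may contain many zeros; the direction follows from the design.

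The registration wording is a smaller point: it is ambiguous and should be reconciled. In an exploratory pilot the whole is a worthwhile, inexpensive correction, and it does not call the study's validity into question.

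**What to change.** 1. In objective 7 and section 8.2, state that the dose-CAC correlation uses current CAC (for example log(CAC+1)) adjusted for the pre-treatment CAC score, in irradiated patients with a scoreable pre-treatment CT. Show beside it the unadjusted correlation in all irradiated patients, and report how many baseline scans could be scored.
2. Do not offer the change score as an equivalent. At a baseline-current correlation of 0.5 it does no better than current CAC, in power or in false positives.
3. In section 8.2, reconcile the Cardiac CT imaging and Radiotherapy treatment plan paragraphs on which CT is registered to the planning CT: the pre-treatment diagnostic scan, the current cardiac scan, or both.

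**Cost.** These are wording changes, with no extra visit or scan, and the baseline score is already planned. Patients without a usable pre-treatment CT drop out of the adjusted analysis, which can use up the gain in power. Scans from patients treated in 2000-2012 may score less reliably, which would leave the adjustment incomplete. Showing both correlations with their patient numbers lets a reader judge this.
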